Applications of dual energy CT for improving staging and monitoring of therapy response in patients with osseous metastases from castrate-resistant prostate cancer

DUKE CANCER INSTITUTE

A National Cancer Institute-designated Comprehensive Cancer Center

Sponsor: PI – Duke Cancer Institute
Funding Source: Society of Abdominal Radiology
Protocol Source: PI - Duke Cancer Institute
Duke IRB#: Pro00078046

Principal Investigator

[name], M.D.
Dept of Radiology
[name]
[name]
[name]
[name]
Fax

[contact]

Co-Principal Investigator(s)

Name, degree
Email address

Sub-Investigator(s)

[name], MD PhD
[contact]
[name], MD, MBA
[contact]

Statistician

[name],
Ph.D.
[contact]

Lead Study Coordinator

Name, degree TBS
Email address

Regulatory Coordinator

[name].
[contact]

Data Manager

Name, degree
Email address

Original version: Date 10/10/2016

Amended version Date
1:

Protocol Title:

Pilot study to assess feasibility of using dual energy CT to improve staging and monitoring of therapy response in patients with osseous metastases from castrate-resistant prostate cancer.

Short Title:

Dual energy CT for improving staging and monitoring of therapy response in patients with castrate-resistant prostate cancer.

Purpose of the Study:

To evaluate the capabilities of dual energy CT as a more precise and accurate tool for staging and monitoring of therapy response in patients with osseous metastases from castrate-resistant prostate cancer.

Our working hypothesis is that, by providing quantitative material-specific information of tissue composition, dual energy CT may yield more accurate and precise quantitative information for the staging and monitoring of therapy response in patients with osseous metastases from castrate-resistant prostate cancer. State of the art dual-energy MDCT technology, which is available and routinely utilized at Duke University, relies on simultaneous acquisition of two CT datasets at different energy levels, without increasing patient radiation exposure. The dual energy datasets can be used to calculate conventional CT images, similar to a routine single energy CT acquisition, or they can be further processed to extract material-specific information. The latter datasets have proven to be beneficial in multiple clinical scenarios (2-4).

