Patients with osseous metastases from prostate cancer provide a common clinical and diagnostic challenge. Not uncommonly, subclinical metastatic lesions may only become detectable at imaging in response to therapy due to increased bone deposition during the first three months of post therapy. Commonly used imaging tests (such as CT or bone scan) are unable to reliably differentiate this phenomenon (also referred to as “flare”) from progressive metastatic osseous disease. This diagnostic challenge may have profound negative effects on patient management as it will require multiple additional imaging follow-up studies before an accurate assessment of tumor response can be formulated with appropriate management (Prostate Cancer Clinical Trials Working Group 3 [PCWG3]).

We postulate that dual energy CT may provide additional critical information in this clinical scenario. Specifically, by providing material-specific quantitative information on iodine concentration within tissues, dual energy CT may be able to distinguish between iodine uptake within viable metastatic osseous disease and lack of thereof within treatment-related reactive sclerotic lesions. This differentiation may not be possible using conventional attenuation measurements with single-energy CT due to the challenging anatomical environment within the

vertebral body where sclerotic metastatic tissue coexists with the complex structural anatomy of the fine trabecular bone.

Background & Significance:

Prostate cancer (PCA) is the most frequently diagnosed cancer in North America. It is the fourth most common cause of cancer death overall and the third most common cause of cancer death in men. In this cancer, bone represents a preferential site of metastases, and patients with advanced disease have a very high incidence of bone metastases. Autopsy data from prostate cancer patients indicate an incidence of secondary bone lesions as high as 65–75%, preceded only by multiple myeloma. These bone metastases are typically osteosclerotic (i.e. with increased osteoblastic activity), and likely to produce a significant impact on patients' functional status and quality of life, not only related to pain, but also to the relevant risk of skeletal-related events that can negatively impact physical well-being and activities of daily living.

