Castrate-resistant PCA presents a spectrum of disease ranging from rising prostate-specific antigen (PSA) levels in the absence of metastases or symptoms and despite androgen-deprivation therapy, to metastases and significant debilitation from cancer symptoms. Castrate-resistant PCA is usually suspected in patients with new symptoms on androgen deprivation therapy, with a rising PSA, or with new evidence of disease on bone scans or CT scans.

Novel hormonal agents such as abiraterone acetate and enzalutamide improved survival significantly for patients with metastatic castration-resistant prostate cancer. Nevertheless, median survival is limited to 35 months after initiation of therapy. Therefore, it is beneficial to have a more accurate diagnostic measure to assess time to progression, either for patients to receive optimal therapy regimes or for studies to have a more accurate time to progression measure (5, 6). For this reason, the PCWG3 defined criteria for progression of the disease. The most challenging task is the assessment of bone metastases in the early phase of therapy due to common onset of a flare phenomenon. The flare phenomenon refers to the increase in radiotracer uptake at previously diagnosed or new previously undetected lesions soon after initiating therapy. Increased uptake is transient, but variable, lasting between three and six months. It is thought that the increase is a response to bone deposition and repair at treated sites. This increase in signal makes the distinction between progression of bone lesions or increased metastatic spread and successful treatment considerably difficult. In CT scans these lesions would appear osteosclerotic and thus could not be distinguished between therapy response and progression. For this reason, the PCWG3 defined progression as “appearance of at least two new lesions on first post-treatment scan, with at least two additional lesions on the next scan (2+2 rule). If at least two additional new lesions are seen on the next (confirmatory) scan, the date of progression is the date of the first post-treatment scan, when the first two new lesions were documented.” This implicates that progression needs to be dated back and diagnosis of progression is delayed by three months typically.

This highlights the critical need to precisely and accurately determine between flare and progressive disease after onset of therapy.

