To demonstrate the feasibility to monitor metastatic bone disease in castration resistant prostate cancer more accurately than regular single energy CT, single phase dual energy CT and technetium bone scans a quantitative analysis of iodine uptake will be performed. ROC statistics will be calculated to find optimal threshold of this biomarker. Qualitative analysis will be done by multiple readers in blinded fashion to determine sensitivity and specificity for distinction between disease progression at first follow-up three month after initiation of therapy. Findings will be correlated with technetium based bone scans.

To analyze the feasibility to detect bone metastasis at baseline more accurately, unenhanced bone marrow imaging will be calculated and additional dual energy based, calcium corrected iodine maps will be used to determine a threshold for detection of vital bone metastasis in order to calculate color coded bone maps for risk of presence of bone metastases. Qualitative analysis will be done by multiple readers in blinded fashion to determine sensitivity and specificity.

To analyze iodine uptake of soft tissue metastasis more accurately and monitor its change during therapy, a ROI based analysis will be performed for suspect metastatic lesions at three time points to see effects of therapy and to distinguish between partial remission, stable disease and progressive disease. A blinded multi reader assessment of iodine maps will be performed to calculate sensitivity and specificity for qualitative analysis of dual energy based examination compared to single-energy CT.

As an exploratory objective we want to determine whether dual energy CT has prognostic capabilities when assessing bone marrow metastases and soft tissue metastasis in terms of therapy response and overall survival. This exploratory objective will require long term follow up and access to patient data exceeding the time period of the baseline and first two follow up CT examinations. Caplan Mayer curves will be drawn and correlated with findings of bone marrow analysis.

Another exploratory objective is to correlate whether adjusted iodine quantification is a viable biomarker for early detection of lymph node metastases, which are too small to fulfill RECIST criteria of a metastasis at baseline but will become evident on follow up. A ROI analysis will be performed to assess whether adjusted iodine uptake might be a viable biomarker for early detection of lymph node metastases.

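### The primary ROC, sensitivity and specificity for progression at first follow-up have no stated reference standard, and the bone scan cannot supply one for a claim of greater accuracy

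*Combined protocol and SAP*

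**What the plan says.** The primary-objective paragraph of Section 5 (Data Analysis & Statistical Considerations) sets out to show that dual energy CT monitors bone disease "more accurately than regular single energy CT, single phase dual energy CT and technetium bone scans". It plans ROC statistics to find a threshold for iodine uptake, and a blinded multi-reader assessment of "sensitivity and specificity for distinction between disease progression at first follow-up three month after initiation of therapy". Its last sentence is "Findings will be correlated with technetium based bone scans". It names no reference standard.

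Other sections bear on the gap:

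- **Purpose of the Study**, on flare: "Commonly used imaging tests (such as CT or bone scan) are unable to reliably differentiate this phenomenon" from progressive bone disease.
- **Primary Objective**: single energy CT and the bone scan are the tests to be improved upon.
- **Background & Significance**: describes the PCWG3 2+2 rule, under which progression is confirmed at the next scan and dated back. On flare it says "Increased uptake is transient, but variable, lasting between three and six months".
- **Design & Procedures**: schedules dual energy scans at baseline and at first and second follow-up, to separate partial remission, stable disease and progression.

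The baseline-detection paragraph of Section 5 says "Qualitative analysis will be done by multiple readers in blinded fashion to determine sensitivity and specificity" and names no truth. The soft-tissue paragraph plans "to calculate sensitivity and specificity for qualitative analysis of dual energy based examination compared to single-energy CT".

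**The concern.** An ROC curve, a sensitivity and a specificity each compare a test result with a known status. Without a rule for that status they cannot be computed, and the primary question of greater accuracy cannot be answered as worded.

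The bone scan is the only test tied to the primary findings, and it cannot carry the claim. If it became the truth, its own sensitivity and specificity would be 100% by construction and no rival could beat it. It would also be judging the very distinction that the protocol says it cannot make reliably.

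If the label is left open until the reads exist, it can be chosen, even in good faith, to suit them. The choice of non-progressors matters too: specificity against flare cases alone can differ widely from specificity against everyone without progression.

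**Working it through.** The documents give no expected accuracy, progression rate, error rate or power, so there is no figure to reproduce. The main check is a reading of the text.

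**1. What each measure needs, and what is stated.**

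| Element | Stated for the primary analysis? |
|---|---|
| Index test | Yes: iodine uptake and blinded reads |
| Comparators | Yes: single energy CT, single phase dual energy CT, bone scan |
| Positive class | Yes: progression at first follow-up |
| Negative class | Not stated; flare is implied by the Purpose and Background sections |
| How true status is set | Not stated |
| Unit (lesion or patient) and lesion-to-patient rule | Not stated |

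**2. Candidate references.** The bone scan is excluded for the reasons given above. The 2+2 rule and the second follow-up could supply a label, but the rule appears only as background. The second scan's stated purpose is response classification, and no section makes either one the truth for the first-follow-up reads.

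**3. Illustrations.** All rates below are assumed. Progression is 10–50% throughout, and the finding does not depend on these figures.

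*(a) Only if the three-month bone scan became the truth, which the plan does not say.* Let p be the progression rate, and let the bone scan have sensitivity 0.90 and specificity s from 0.50 to 0.90. Its errors are assumed unrelated to iodine uptake within each true class. A perfect test then shows:

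- apparent sensitivity = 0.90p / [0.90p + (1−p)(1−s)]. At p = 0.10, s = 0.50: 0.09/(0.09 + 0.45) = 17%. At p = 0.50, s = 0.90: 0.45/(0.45 + 0.05) = 90%.
- apparent specificity = (1−p)s / [(1−p)s + 0.10p]. At p = 0.50, s = 0.50: 0.25/(0.25 + 0.05) = 83%. At p = 0.10, s = 0.90: 0.81/(0.81 + 0.01) = 99%.
- apparent AUC = the mean of the two, which runs from 0.57 (p = 0.10, s = 0.50) to 0.90 (p = 0.50, s = 0.90).

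*(b) Choice of negative class.* Suppose specificity is 0.60 in flare and 0.95 in other non-progressors, with flare share f. Specificity is 0.60 against flare alone. Against all non-progressors it is 0.60f + 0.95(1−f), which gives 0.88, 0.81 and 0.74 for f = 20%, 40% and 60%.

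*(c) Precision of a later-status label.* The protocol says that 150 patients will be contacted, which is a ceiling on enrolment. At 10–50% progression there are at most 15–75 progressors. With 80% correct, exact 95% intervals for sensitivity are 52–96% (12/15) and 69–88% (60/75).

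*(d) Unclassified patients.* Suppose U = 15 or 30 of 150 have no label, P = 10% or 50% of the rest progress, and sensitivity among those classified is 80%. If all U progress, sensitivity is 0.8P/(P+U) when they all test negative and (0.8P+U)/(P+U) when they all test positive.

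| U | P | All test negative | All test positive |
|---|---|---|---|
| 15 | 13.5 | 38% | 91% |
| 15 | 67.5 | 65% | 84% |
| 30 | 12 | 23% | 94% |
| 30 | 60 | 53% | 87% |

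These are the widest limits for all-progressor assignment. Limits built on the observed reads would be narrower.

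**The case against.** The strongest reply is that the intention can be inferred. The Purpose and Background sections are about flare versus progression, so the primary sentence looks like a drafting slip with words missing. The 2+2 rule is described, a second follow-up is scheduled, and the lymph-node paragraph already uses later status as truth by looking at nodes that become evident on follow-up. The title also calls this a "Pilot study to assess feasibility of using dual energy CT to improve staging and monitoring of therapy response".

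Part of this stands:

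- A reader might infer that the contrast is wholly undefined. The documents do not support that, since flare is the natural second class. What stays open is whether non-progressors without flare are counted.
- A reader might infer that the plan treats the bone scan as truth. It says only that findings will be correlated with it.
- A reader might infer that the protocol calls the bone scan unreliable in general. The statement is confined to flare versus progression and covers CT as well, though that is the primary task.
- A reader might infer that the soft-tissue analysis is silent on truth. Its wording is ambiguous instead: single-energy CT could be comparator or reference.

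The rest does not stand. An implied rule that no section ties to the primary analysis is not a prespecified label. Pilot status excuses wide intervals, but it does not supply a status against which to count right and wrong answers, and the primary analysis is worded as an accuracy comparison.

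**Conclusion.** The concern holds and should be fixed before any images are read. No reference standard is stated for the primary ROC, sensitivity and specificity. The bone scan, as a comparator with an acknowledged weakness on this exact distinction, cannot support a claim of greater accuracy through correlation. The baseline-detection paragraph has the same gap, and the soft-tissue paragraph needs clarifying.

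The size is categorical, not numerical: the measures are undefined as written. This rests on the text alone. The documents do not show that a label will be picked after the fact, only that nothing prevents it.

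**What to change.** **Primary label.** Before images are read, prespecify confirmed versus not confirmed bone progression, set at the second follow-up. The PCWG3 2+2 rule in Background & Significance is the default because the protocol already cites it and dates progression back to the first post-treatment scan. Another named later-status label, independent of the dual energy reads, is acceptable. Assign it from existing clinical reports, without sight of the iodine maps.

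**Analysis.**

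- Use the label for the ROC, and for sensitivity and specificity of dual energy, single phase dual energy and single energy CT.
- State how lesion iodine values become one value per patient.
- Among patients with at least two new bone-scan lesions at first follow-up, report later-confirmed and presumed-flare cases separately, with exact confidence intervals.
- Report patients with fewer than two new lesions at first follow-up who progress later as their own group, in a sensitivity analysis.
- If the label includes the first bone scan, claim no sensitivity or specificity gain over bone scan. Keep the correlation as descriptive agreement.
- Report patients without a second follow-up or bone scan as unclassified, with true worst-case and best-case bounds. For sensitivity, the worst case assigns unclassified test-negatives to progression and test-positives to non-progression, and the best case reverses this. Specificity is treated likewise.

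**Other analyses.** For baseline detection and soft tissue, name the truth source, or report agreement only.

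**Cost.** A text change and a blinded labelling step, with no extra CT. Bone-scan availability at each time point must be confirmed first, because the protocol gives no bone-scan schedule. The label waits for the second follow-up, whose timing should be stated, and may still contain some flare given the three-to-six-month window. The flare subgroup will be small, and under the 2+2 label the superiority claim over bone scan is given up.

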State of the art dual-energy CT enables simultaneous acquisition of two CT datasets at different energy levels *without* exposing patients to additional radiation dose. These datasets can be used to reconstruct regular CT images of identical image quality compared to conventional single-energy CT or facilitate further processing of dual-energy material-specific density images. Preliminary evidence suggest that material density images may improve detection of lithic metastatic lesions, such as in patients with multiple myeloma (7). However, the diagnostic accuracy of material density analysis in patients with sclerotic osseous metastases (such as patients with PCA) remains to be investigated. This is a particularly challenging task due to bone mineral deposition within primarily osteosclerotic metastatic lesions, remodeling of bone due to therapy response, and the complex structural anatomy of the trabecular bone within the vertebral bodies.

Our working hypothesis is that, by providing quantitative material-specific information of tissue composition, dual energy CT may yield more accurate and precise quantitative information for the staging and monitoring of therapy response in patients with osseous metastases from castrate-resistant prostate cancer.

Purpose of this study

Primary Objective:

Demonstrate the feasibility of using dual energy CT to improve staging and monitoring of therapy response in patients with osseous metastases from castrate-resistant prostate cancer, compared to regular single energy CT and technetium bone scans.

Secondary Objectives:

Analyze the feasibility to detect bone metastasis at baseline more accurately.

Analyze iodine uptake of soft tissue metastasis more accurately and monitor its change during therapy.

Correlate whether iodine quantification is a viable biomarker for early detection (small size) of lymph node metastases.

Exploratory Objective:

Determine whether dual energy CT is able to have prognostic capabilities in terms of therapy response and overall survival.

Design & Procedures:

This is a prospective Health Insurance Portability and Accountability Act-compliant study for which we are asking for authorization from the Institutional Review Board.

Inclusion Criteria:

1. Oncology patients with castrate-resistant prostate cancer planned for therapy with abiraterone acetate or enzalutamide and prednisolone undergoing clinically indicated MDCT of the chest, abdomen and pelvis
2. > 18 years old

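### The bone analysis aims at better accuracy than technetium bone scan, but names no reference for progression and only says findings will be correlated with bone scans

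*Combined protocol and SAP*

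**What the plan says.** The Primary Objective is to demonstrate feasibility of improved staging and monitoring "in patients with osseous metastases from castrate-resistant prostate cancer, compared to regular single energy CT and technetium bone scans". The bone paragraph of Data Analysis & Statistical Considerations repeats this as monitoring bone disease "more accurately than regular single energy CT, single phase dual energy CT and technetium bone scans".

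That paragraph then lists four pieces of work:

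- a quantitative analysis of iodine uptake;
- ROC statistics to choose a threshold;
- a blinded multi-reader assessment "to determine sensitivity and specificity for distinction between disease progression at first follow-up three month after initiation of therapy";
- a closing sentence on bone scans, which reads "Findings will be correlated with technetium based bone scans".

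The last item is the only analytic use of bone scans stated anywhere. The other mentions are background or part of an objective. The reader item does not say which modalities are read or what establishes progression.

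Three other places bear on the point. Purpose of the Study says "Commonly used imaging tests (such as CT or bone scan) are unable to reliably differentiate this phenomenon", meaning flare as against progression. Background & Significance says of flare: "Increased uptake is transient, but variable, lasting between three and six months". It also gives the working-group definition of progression, "appearance of at least two new lesions on first post-treatment scan, with at least two additional lesions on the next scan (2+2 rule", but the analysis section does not adopt that rule as its reference.

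**The concern.** A statement that one test is more accurate than another needs both tests scored against the same truth. Here the truth is not named, and bone scan enters only through a correlation. Correlation describes how often two tests agree. It does not say which one is right when they disagree.

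The protocol's own argument makes this important. If bone scan cannot separate flare from progression, a test that can must disagree with bone scan in flare patients. Success would then lower the planned statistic, and so would a failure of the opposite kind, such as missing real progression. If bone scan is instead meant as the yardstick, its accuracy is 100% by definition and dual-energy CT cannot be shown to improve on it.

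The gap is wider than bone scan. The bone paragraph gives no explicit method for comparing with single-energy CT or single-phase dual-energy CT either. The pilot could therefore finish without knowing whether dual-energy CT does better or worse than the tests named in its primary objective.

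**Working it through.** The documents give no accuracy figures, effect size or sample-size calculation, so there is no stated figure to reproduce. The inputs below are assumptions, except the 150 patients to be contacted (Consent Process).

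**1. What agreement allows.** For two yes/no tests in the same N patients, let b and c be the two kinds of discordant patient. In each discordant patient exactly one test is right. The accuracy difference therefore lies between −(b+c)/N and +(b+c)/N, that is ±(1 − agreement), within limits set by bone scan's own errors.

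- Agreement 90%: up to 10 points either way.
- Agreement 80%: up to 20 points either way.
- Agreement 70%: up to 30 points either way.

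**2. An example with identical correlation.** Assume 100 patients, 40 of whom progress. Bone scan has sensitivity 90% and specificity 60%: TP 36, FN 4, FP 24, TN 36, accuracy (36+36)/100 = 72%.

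- Test A corrects 20 of the flare false positives: TP 36, FP 4, TN 56, accuracy (36+56)/100 = 92%.
- Test B misses 20 true progressions: TP 16, FP 24, TN 36, accuracy (16+36)/100 = 52%.

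The cross-table with bone scan is the same for both: both positive 40, bone scan only 20, new test only 0, both negative 40.

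- phi = (40×40 − 20×0)/√(60×40×40×60) = 1600/2400 = 0.67.
- kappa = (0.80 − 0.48)/(1 − 0.48) = 0.62.
- With bone scan as yardstick, both tests score sensitivity 40/60 = 67% and specificity 40/40 = 100%.

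One test is 20 points better than bone scan and the other 20 points worse. No statistic built only from the cross-table with bone scan separates them.

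**3. The 2+2 rule as reference.** Suppose it is applied to the same bone-scan readings, with a positive first scan meaning two or more new lesions.

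- Every reference-positive patient is bone-scan positive at first follow-up, so bone-scan sensitivity is 100% by construction.
- Every patient with fewer than two new lesions on that scan is reference-negative. A true progressor missed by bone scan (4 in the example) counts as a bone-scan true negative, and as a false positive for any CT reading that detects it.

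Both measures are affected, so specificity alone is not a safe comparison.

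**4. Precision of a paired comparison.** Half-width = 1.96 × √((d − δ²)/n), with discordance d = 0.20 and difference δ = 0.10.

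- n = 150: 1.96 × √(0.19/150) = 0.070.
- n = 120: 1.96 × √(0.19/120) = 0.078.
- n = 90: 1.96 × √(0.19/90) = 0.090.

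**The case against.** The strongest reply is that the plan already contains what is needed. Reader sensitivity and specificity for progression are planned, and they would separate Tests A and B at once (90% and 93% against 40% and 60%). Any reference good enough to score the readers could also score bone scans in the same patients. This stands in part: given a usable reference, the bone-scan comparison is an unlisted calculation. But no reference is named, so the reply relies on something the plan does not supply.

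A reader might infer several stronger points that the documents do not support:

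- **That the study cannot answer its question.** This takes *correlated* literally. The protocol uses the word loosely elsewhere, for survival curves and for the lymph-node biomarker, so an accuracy comparison may have been meant. The soft-tissue paragraph plans "to calculate sensitivity and specificity for qualitative analysis of dual energy based examination compared to single-energy CT", so comparative wording is used in places, but no objective makes bone scan a comparator for soft tissue and the contrast is weak evidence.
- **That bone-scan accuracy is excluded.** The reader sentence is silent on modalities, and silence is not exclusion.
- **That bone scans will not be collected.** The data list in Design & Procedures is illustrative and could cover them. The Risk/Benefit count concerns added CT exposure, where routine-care bone scans would not appear.
- **That a formal superiority test is required.** Title, objective and analysis are all framed as feasibility. Estimates with intervals are enough.

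**Conclusion.** The concern holds in a limited form and should be fixed. The primary objective and bone analysis name comparators to be improved on in accuracy, but the plan gives no reference, no list of modalities read, and for bone scan only a correlation. Read as written, the correlation determines neither the size nor the sign of the accuracy difference; at 80% agreement it is compatible with 20 points in either direction. That range follows from arithmetic on paired binary results. The 92% and 52% example rests on assumed prevalence and bone-scan accuracy, and only shows that the range can be reached.

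Confidence is moderate, because the authors may have intended a comparison that they did not write down. The underlying defect is the missing common reference, of which the correlation sentence is the clearest symptom.

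**What to change.** Replace the correlation sentence with a descriptive paired accuracy comparison:

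1. Name one reference for progression at first follow-up that does not depend on the readings being compared, for example status established from the clinical record and later follow-up. If the clinical record contains the bone-scan report being scored, say how that report is set aside.
2. Score dual-energy CT, single-energy CT, single-phase dual-energy CT and the available bone scans against it in the same patients. Report sensitivity, specificity and paired differences with 95% confidence intervals.
3. State where the bone scans come from. Report the CT-to-bone-scan interval, since flare changes over time, and the number of patients without a paired scan.
4. If a bone-scan-based 2+2 rule is used as reference, state that it biases both sensitivity and specificity, and treat that comparison as secondary.

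The cost is a rewritten paragraph plus some analysis and adjudication. Eligibility does not change. Existing bone-scan results can be used, so no extra scans or readers are required where those results are available. The documents do not say whether bone scans come from routine care.

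The downside is a denominator limited to patients with paired scans. The 150 in the protocol are patients to be contacted, so the paired number may be smaller. Under the assumptions in the working, a 10-point difference would have an interval of about 3 to 17 points at 150 and 1 to 19 at 90, which is adequate for a pilot estimate.
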